10.9.1.2 Analysis Sets

Safety Set: All randomised participants who receive at least 1 dose of IMP will be included in the Safety Set.

PD Set: All randomised participants who receive at least 1 dose of IMP and have at least one post-baseline antibody concentration will be included in the PD Set.

Per Protocol Set: The Per Protocol Set will be comprised of all participants in the PD Set who comply with the following criteria:

- Do not have an occurrence of vomiting or diarrhoea which may impact the systemic exposure of IMP;
- Do not use a concomitant medication which may impact the immunogenicity results;
- Do not incur a major protocol deviation which may invalidate or bias the immunogenicity results.

10.9.1.3 Description of Statistical Methods

All statistical analysis will be performed using SAS® (version 9.3 or higher).

Descriptive statistics for quantitative parameters will be provided using number of observations (N), mean, standard deviation (SD), minimum, median and maximum. Descriptive statistics for qualitative parameters will be provided using absolute frequencies (n) and relative frequencies (%). For immunological endpoints (IgG, IgA, concentrations and fold increase) additionally geometric means with corresponding 95% confidence intervals (CI) will be presented.

For parameters with evaluation before vaccination and in case of repeated value(s), only the last observation prior to dosing will be used in descriptive and inferential statistics and derivations of other parameter values. After vaccination, only values of scheduled assessments (planned in the protocol) will be used.

10.9.1.3.1 Demographic and Background Data

All demographic and background data will be listed, in addition:

Disposition: Participant disposition will be listed with any withdrawals flagged. Frequencies (number and %) of the total number of participants dosed, completed and prematurely discontinued (including reason for discontinuation) from the study will be summarised by treatment and overall (all treatments combined). Additionally, the number and percentage of participants included within each analysis set will be summarised.

Demographics: Demographic data will be listed. Descriptive statistics (number of participants in the analysis set (N), number of participants with non-missing observations (n), mean, standard deviation (SD), minimum, median and maximum) will be tabulated by treatment and overall for the continuous variables age, height, weight and BMI and frequencies (number and %) for the categorical variables race and gender.

10.9.1.3.2 Efficacy Data

Not applicable.

10.9.1.3.3 Safety Data

All safety data will be listed, in addition:

AEs: All AEs will be coded using the Medical Dictionary for Regulatory Activities (MedDRA) dictionary (the most up to date version will be used and this will be documented in the DMP)

All AEs, including those which occurred prior to receiving the first dose of IMP, will be listed. Only treatment emergent adverse events (TEAEs), i.e., existing conditions that worsen or events that occur during the course of the study after administration of IMP, will be included within the summary tables. AE summaries will be presented by treatment, all active treatments combined and overall.

An overall summary of AEs will be produced including the number of TEAEs; the number and % of participants reporting at least 1 TEAE, serious TEAE, TEAE leading to withdrawal from the study; the number and % of participants reporting TEAEs by severity and relationship to IMP.

The number of TEAEs and the number and % of participants reporting at least 1 TEAE will be tabulated by system organ class (SOC) and preferred term. A participant reporting multiple episodes of a particular AE will only contribute 1 count towards the corresponding SOC and preferred term.

The number of TEAEs and the number and % of participants reporting at least 1 TEAE will be tabulated by preferred term and sorted by descending frequency on the total number of participants with that AE. A participant reporting multiple episodes of a particular AE within a treatment period will only contribute 1 count towards the corresponding preferred term.

In addition, the number and % of participants reporting TEAEs will be tabulated by maximum severity and strongest relationship to IMP. For the summary of TEAEs by severity, if a participant has multiple events occurring within the same SOC or preferred term the event with the highest severity will be counted. Similarly, for TEAEs by relationship to IMP, if a participant has multiple events occurring within the same SOC or preferred term, the event with the highest association to IMP will be counted.

The incidence of TEAEs will be compared between treatments using Fisher's Exact Test (or an alternative statistical test if appropriate).

Laboratory Safety: Biochemistry, haematology, and urinalysis parameters will be listed with any out of normal range values flagged. Laboratory test results which are out of normal range will also be presented separately along with normal reference ranges. Descriptive statistics (N, n, mean, SD, minimum, median and maximum) of absolute and change from baseline (Day 0) values at each protocol-defined time-point will be tabulated by treatment.

Vital Signs: Vital signs parameters will be listed with any out of normal range values flagged. Descriptive statistics (N, n, mean, SD, minimum, median and maximum) of absolute and change from baseline (Day 0 pre-dose) values at each time-point will be tabulated by treatment.

12-Lead ECG: 12-Lead ECG parameters will be listed with any out of normal range values flagged.

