Safety follow-up telephone calls will be performed on Days 154 and 224 following the first dose of study vaccine administration to check the general health of the participant and to review clinically relevant AEs. Clinically relevant adverse events are adverse events that required a visit to a healthcare professional. Assessments will be performed as per [Table 10.7.1](#).

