10.7.1.3.1 Adverse Events

AEs and SAEs that occurred during the study along with their severity and relationship to study drug will be reported.

An AE is defined as per Statutory Instrument 2004 No. 1031^[4]:

Any untoward medical occurrence¹ in a participant to whom a medicinal product has been administered, including occurrences which are not necessarily caused by or related to that product.²

Notes:

¹ Whether subjective complaint or objective finding.

² An AE can therefore be any unfavourable and unintended sign (including an abnormal laboratory finding), symptom, or disease temporarily associated with the use of an IMP, whether or not considered related to the IMP.

An unexpected adverse reaction is defined as:

An adverse reaction, the nature, or severity of which is not consistent with the applicable product information (e.g., Investigator's brochure for an unapproved investigational product or summary of product characteristics (SmPC) for an authorised product).

AEs will be monitored throughout the study from the signature of participant informed consent through to the post-study follow-up visit. All AEs will be recorded, whether considered minor or serious, drug-related or not.

All abnormal laboratory findings considered to be clinically significant will be recorded as AEs.

Recording of Adverse Events

All of the following details will be recorded in the participant's eCRF for each AE:

- Full description of AE.
- Date and time of onset.
- Date and time of resolution.
- Severity of event to be assessed by an Investigator in accordance with the definitions below.
- Relationship to IMP to be assessed by an Investigator in accordance with the definitions below.
- Action taken (if any).
- Outcome and details of any further follow-up.

Grades of Adverse Event Severity

The following grades will be used by an Investigator to describe the severity of AEs.

The following are the only grades, which will be used to describe AE severity. Only 1 severity grade will be used for each AE (e.g., mild - moderate is not acceptable).

SEVERITY OF THE AE	DEFINITION
Mild	The AE does not interfere with the participant's daily routines. It causes no more than slight discomfort or mild objective change in any of the safety parameters assessed during the study as determined by the Investigator.

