10.9.1.1 Study Variables/Endpoints

Primary Endpoint

- Local and systemic reactogenicity up to Day 84 as assessed by adverse events, laboratory safety tests (biochemistry, haematology, urinalysis), vital signs and physical examination.

Secondary Endpoints

- Local and systemic reactogenicity; from Day 85 to Day 224 as assessed by adverse events, laboratory safety tests (biochemistry, haematology, urinalysis) if undertaken for cause; vital signs if undertaken for cause; physical exam if undertaken for cause.
- Concentrations of specific serum IgA and IgG antibodies to LPS O:2 and O:9, flagellin H:a and H:d.
- Fold increase in specific serum IgA and IgG antibody concentrations, in individual participants, against the antigens LPS O:2 and O:9, flagellin H:a and H:d.
- Concentrations of specific mucosal IgA antibodies in lymphocyte supernatant (ALS) assays, in individual participants, against antigens LPS O:2 and O:9, flagellin H:a and H:d.
- Seroconversion rate (proportion of participants with 4-fold increase above baseline at any time post vaccination) against each of the above antigens.
- Fold increase in specific mucosal IgA antibodies in lymphocyte supernatant (ALS) assays, in individual participants, against the antigens LPS O:2 and O:9, flagellin H:a and H:d.

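### The TEAE tables and Fisher comparison have no Day 84 cut-off, so the adverse-event part of the primary endpoint is pooled with the Day 85–224 secondary endpoint

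*Combined protocol and SAP*

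**What the plan says.** Section 10.9.1.1 lists two safety endpoints with adjoining windows. The primary is "Local and systemic reactogenicity up to Day 84 as assessed by adverse events, laboratory safety tests", together with vital signs and physical examination. The secondary is "Local and systemic reactogenicity; from Day 85 to Day 224 as assessed by adverse events", plus laboratory tests, vital signs and physical examination if done for cause. The primary objective in 9.1 also stops at Day 84.

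Section 10.9.1.3.3 defines the events that enter the summary tables: conditions that worsen, or "events that occur during the course of the study after administration of IMP, will be included within the summary tables". No end day is given. The tables (overall summary, system organ class and preferred term, severity, relationship) are presented by treatment, for all active treatments combined, and overall. The comparison is stated in the same open way: "The incidence of TEAEs will be compared between treatments using" Fisher's exact test or an alternative, with no time window.

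On collection after Day 84, section 10.1 provides telephone calls on Days 154 and 224 to check general health and review clinically relevant events, and adds: "Clinically relevant adverse events are adverse events that required a visit to a healthcare professional". Section 10.7.1.3.1 runs adverse-event monitoring from consent through post-study follow-up, and says: "All AEs will be recorded, whether considered minor or serious, drug-related or not".

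**The concern.** An endpoint defined on a window needs an analysis on that window. Here the endpoint section splits safety at Day 84/85 and the analysis section does not, so a programmer following 10.9.1.3.3 literally would produce one set of tables running to the Day 224 call. The reader of the study report could not take from those tables the incidence of adverse events for either the primary or the secondary endpoint.

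The two periods also differ in how events are found. Days 0–84 have 12 scheduled visits. Days 85–224 have two telephone calls, and the protocol gives two rules for what the calls capture. Late events that are unrelated to vaccination and equally common in each arm raise both incidences and shrink the difference between vaccine and placebo. If the window is left open until the tables are programmed, it can also be chosen after data have accrued.

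**Working it through.** **Inputs from the protocol.** Windows: 10.9.1.1. TEAE definition and comparison: 10.9.1.3.3. Visits and calls: 10.1 and Table 10.7.1. Cohorts 9 + 18 + 18 = 45, of whom 6 + 12 + 12 = 30 receive vaccine and 3 + 6 + 6 = 15 placebo. The protocol states no power, alpha or expected event rate (10.9.2), so there is no planned figure to reproduce.

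**Do the tables really run past Day 84?** The synopsis gives about 36 weeks per participant. Screening of 28 days plus 224 days is 252 days, and 252/7 = 36.0 weeks. The study therefore includes the Day 224 call, and so does the TEAE definition.

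**Share of the window outside the primary endpoint.** Days 0–84 are 85 days. Days 85–224 are 224 − 85 + 1 = 140 days. 140/225 = 62%. This is a share of nominal calendar time, not of events.

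**Which components are affected?** Laboratory values and vital signs are tabulated by treatment at each time-point (10.9.1.3.3). Table 10.7.1 schedules none after Day 84, and 10.9.1.3 uses only scheduled values after vaccination. Those tables therefore already respect Day 84. Physical examination has no summary described beyond listing. The mismatch lies in the adverse events.

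**Effect of pooling on the any-TEAE difference.** Let p be the incidence to Day 84 and b the proportion with an event in Days 85–224, equal in both arms and independent of early events. The pooled incidence is 1 − (1 − p)(1 − b), so the pooled difference is (p₁ − p₂)(1 − b). With p₁ = 50% and p₂ = 25% (assumed):

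| b (assumed) | Vaccine | Placebo | Difference |
|---|---|---|---|
| 0 | 50% | 25% | 25 points |
| 5% | 52.5% | 28.75% | 23.75 points |
| 10% | 55% | 32.5% | 22.5 points |
| 20% | 60% | 40% | 20 points |
| 30% | 65% | 47.5% | 17.5 points |

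**Effect on the Fisher comparison.** Power was found by summing binomial probabilities over every table with two-sided p ≤ 0.05. Placebo is pooled across cohorts (n = 15), and p₁ = 60%, p₂ = 20%. The rates, alpha, sidedness and pooling are all assumptions.

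| b | Difference | 12 vs 15 | 30 vs 15 |
|---|---|---|---|
| 0 (Day 84 table) | 40 points | 0.464 | 0.669 |
| 10% | 36 points | 0.360 | 0.553 |
| 20% | 32 points | 0.285 | 0.465 |
| 30% | 28 points | 0.236 | 0.387 |

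**Precision.** With zero events, the two-sided exact 95% upper limit is 1 − 0.025^(1/n): 46% for n = 6, 26% for n = 12 and 12% for n = 30.

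**The case against.** The strongest reply is that nothing is lost. Onset dates are recorded (10.7.1.3.1), all adverse events are listed, and a separate SAP is still to be agreed before database lock (10.9.1) and could add the split. That is right as to recoverability and makes the repair cheap. It does not remove the gap, because no text in the protocol requires the split.

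It might also be said that 10.9.1.3.3 already refers to a treatment period, which footnote 1 of Table 10.7.1 defines as Day 0 to Day 84: "A participant reporting multiple episodes of a particular AE within a treatment period will only contribute 1 count". That sentence only governs how repeat episodes are counted in one preferred-term table. It does not drop later events, and the counting rule for the system organ class table has no such limit.

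The size of the dilution is fairly disputed. No document gives a late-event rate for screened healthy adults, and at 5% the loss is little more than one point. Tables by preferred term and by relationship to IMP would also separate out many unrelated late events.

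Four stronger readings are tempting, and the documents do not support them:

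- *The primary endpoint is never tabulated.* Its laboratory and vital-sign components are, by time-point to Day 84.
- *Collection switches to medically attended events after Day 84.* Section 10.1 points that way and 10.7.1.3.1 says otherwise. This is a conflict, not a settled rule.
- *Reactions to repeated doses are lost.* Participants count once per term, but the number of TEAEs is tabulated too, and laboratory values are tabulated one week after each dose (Days 7, 28 and 49). What is missing is an adverse-event table by dose.
- *Fisher's test is an error because power is low.* For 40% versus 10% (assumed), power is 32% for 12 vs 15, 9% for 12 vs 6 and 3% for 6 vs 3, but 52% for all active versus pooled placebo (30 vs 15). The plan claims no power, so preferring intervals to p-values is a matter of judgement.

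**Conclusion.** The point holds for the adverse-event component. The TEAE tables and the Fisher comparison carry no Day 84 boundary, so the primary and secondary adverse-event endpoints are merged and neither is summarised or compared on its own window. This follows from the text alone and needs no assumption. The disagreement between 10.1 and 10.7.1.3.1 is also plain on the page, and it leaves unclear what the late part of the pooled tables would contain.

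The numerical consequence is conditional. Under equal and independent late-event rates of 5% to 30%, an assumed 25-point difference shrinks by 1.25 to 7.5 points. Unequal late rates could move the pooled difference either way. The absence of by-dose tables and confidence intervals for incidences is a matter for improvement, not a contradiction in the plan.

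**What to change.** In 10.9.1.3.3, and in the SAP when written:

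1. Produce the TEAE tables and the between-treatment comparison for events with onset in Days 0–84, identified as the primary endpoint analysis.
2. Produce them separately for onset in Days 85–224, identified as the secondary endpoint analysis.
3. State whether the boundary is the calendar day or the Day 84 visit, since Table 10.7.1 allows that visit a window of 7 days either side.
4. Reconcile 10.1 and 10.7.1.3.1 on which events are collected after Day 84, and label the late table with what was actually collected.

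Two optional additions use data already held: TEAEs tabulated by preceding dose, which would speak directly to the three-dose objective; and exact 95% confidence intervals for each incidence and each active-minus-placebo difference, shown alongside the Fisher p-values.

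The cost is protocol and SAP wording and a few more tables, with no new data collection for the split. The intervals will be wide, which reflects the sample size. The window should be fixed before the database is locked.

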10.9.1.3.4 PD Data

Descriptive statistics (N, n, arithmetic mean, standard deviation (SD), minimum, median, interquartile range, maximum, geometric mean with corresponding 95% CI) of serum IgG and IgA, mucosal IgA concentrations and fold-increase will be summarised by visit for each treatment group.

The immune response (log-transformed serum IgG and IgA, mucosal IgA concentrations) will be subjected to an ANOVA/ANCOVA to compare pre-vaccination and post-vaccination levels within a treatment group for each visit. Similarly, the immune response (log-transformed serum IgG and IgA, mucosal IgA concentrations) and the magnitude of the immune response (fold-increase) will be compared between treatment groups at each visit.

In addition, the number of participants seroconverting per visit (i.e. with 4-fold increased level above baseline) will be compared between treatment groups using Fisher's Exact Test (or an alternative if appropriate).

10.9.1.3.5 Other Data

Not applicable.

10.9.2 Sample Size Calculation

The sample size chosen for this study is not based on a formal statistical estimation but is considered to be adequate to meet the objectives of the study. A sufficient number of participants will be initially screened for enrolment to ensure that the planned sample size is achieved.

11 PRACTICAL CONSIDERATIONS

11.1 Storage of Data

The Investigator site file and associated study documentation will be archived for at least 25 years after the end of the study (last participant last visit) as per European Medicine Agency Guideline INS/GCP/856758/2018^[15]. The study documentation may be transferred to an offsite storage facility during this period but will remain under the control of Simbec-Orion.

The Sponsor has delegated the set up and maintenance of the Sponsor trial master file (TMF) to Simbec-Orion. The TMF will be returned to the Sponsor at the end of the study, who will archive it for at least 25 years after the end of the study.

11.2 Protocol Amendments

Changes in the study protocol must take the form of written protocol amendments and shall require the approval of all persons responsible for the study (see [Section 1](#)).

A protocol amendment is deemed to constitute a substantial protocol amendment if it is considered to be likely to affect to a significant degree either:

- a. The safety or physical or mental integrity of the participants of the study.
- b. The scientific value of the study.
- c. The conduct or management of the study.
- d. The quality or safety of any IMP used in the study.

Such amendments must be submitted to the REC responsible for the study and the MHRA for approval prior to implementation.

Protocol amendments required for urgent safety reasons may be implemented immediately. However, the REC and MHRA must be notified in writing within 3 days of the measures taken and the reasons for implementation.

All other amendments shall be deemed to be non-substantial and as such do not need the prior approval of the REC and the MHRA.

11.3 Confidentiality

The confidentiality of the study must be maintained at all times and the Principal Investigator must not reveal any information relating to the study without express permission from the study Sponsor.

11.4 Study Report and Publication Policy

Simbec-Orion will investigate and analyse the data generated with all due speed.

A draft study report will be sent to the Sponsor for review. The Sponsor will forward any comments on the draft study report to the Project Manager within 30 days of receipt. Upon receipt of these comments a final, Quality Assurance (QA) approved report will be issued with all due speed. A copy of the report will be forwarded to the Sponsor.

The Principal Investigator will obtain the Sponsor's written permission before any information concerning this study is submitted for publication.

11.5 General Data Protection Regulation

Personal data of the participant shall be processed in a manner that ensures it has appropriate security. This includes protection against unauthorised or unlawful processing and against accidental loss, destruction or damage and by using appropriate technical or organisational measures. One such measure is by the Investigator ensuring that the participants' personally identifiable information should be replaced through the use of pseudonymisation.

On the eCRFs or other documents submitted to Prokarium will NOT be identified by their names but by the assigned participant number (panel/screening/participant number) to ensure confidentiality of the participant's information and that data minimisation principles are maintained. If participant names are included in error on copies of documents submitted to Prokarium, the names will be erased or securely destroyed and the assigned participant number added to the document.

Documents not intended for submission to Prokarium/Simbec-Orion (e.g., signed consent forms) should be maintained by the Investigator in strict confidence and not disclosed to any parties outside of this approved agreement. Forms should be protected by use of strong encryption.

APPENDIX 1: DECLARATION OF HELSINKI (BRAZIL, 2013)

<https://www.wma.net/policies-post/wma-declaration-of-helsinki-ethical-principles-for-medical-research-involving-human-participants/>

